7.2 Emergency management

During this research period, [name] has professional skills and is responsible for medical emergencies and related treatment. If you encounter large-scale or critical events, please report to the head of the department head and hospital timely.

8. Data security and monitoring plan

None.

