The Official Title

A Randomized Controlled Study of Lenvatinib Following Liver Transplantation in
Patients with High-Risk Hepatocellular Carcinoma

NCT number: none

Date of the document: November 16, 2019

Hepatocellular carcinoma (HCC) is the third leading cause of cancer deaths worldwide and accounts for about 13,000 deaths in the United States per year [1]. Liver transplantation offers selected patients with localized HCC a chance for cure. For those meeting the Milan criteria, defined as a single tumor 2–5 cm or three or fewer nodules, each 3 cm or less, and no gross vascular invasion, 5 year survival for transplanted patients is about 75% [2, 3]. Meeting these criteria provides additional priority for transplantation in the US. However, for those with HCC beyond the Milan criteria, whether determined pre-transplant or by pathologic evaluation of the explant, the risk of recurrence may be as high as 70% at 2 years after transplantation [4]. There are few studies evaluating adjuvant therapy after resection or transplantation for HCC, and there is no standard of care for the treatment of these patients. Finding an effective agent which decreases recurrence rates in high-risk patients would be a significant advance.

1. Research Purpose

The aim of this study is to observe the efficacy and safety of lenvatinib in preventing high-risk recurrence of hepatocellular carcinoma patients after liver transplantation.

2. Research Protocol

The research is an open, randomized, single-center study. Patients with high-risk recurrence of hepatocellular carcinoma who underwent liver transplantation are included according to the criteria of admission. After operation, the regimen of calcineurin inhibitors, mycophenolate mofetil, sirolimus or everolimus with glucocorticoids removed at an early stage are used. Patients enrolled in the study were randomly allocated in the lenvatinib group (54 patients) and the control group (54 patients) after stable condition. Patients in the control group are given supportive treatment and regular follow-up. Patients in the lenvatinib group are given lenvatinib within 1-2 months after operation (dose: body weight < 60 kg: 8 mg/day, body weight \geq 60 kg 12 mg/day). The baseline data of patients are collected before allocation. Serum and imaging examination are checked regularly every month to monitor the

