recurrence of hepatocellular carcinoma and the side effects of lenvatinib. The efficacy and safety of lenvatinib in patients of high-risk hepatocellular carcinoma are observed, and the clinicopathological factors affecting the efficacy of lenvatinib are analyzed.

When side effects of lenvatinib occur, the dosage can be reduced according to the patients' condition until discontinuation. When tumor recurrence occurs, a multidisciplinary team will draw up specific treatment plans according to the patients'

condition, including surgical resection, interventional therapy, radiofrequency therapy, radiotherapy and targeted therapy (Patients in the control group can add lenvatinib, and patients in the lenvatinib group can decide whether to continue using it according to the patients' condition).

3. Research population

3.1 This study is a single center clinical study. The cases are from patients with hepatocellular carcinoma who underwent liver transplantation in the liver surgery department of Shanghai Renji Hospital.

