4.4 Follow up

- Once the treatment is initiated, patients will be regularly monitored for blood and imaging examination. Blood test includes alpha-fetoprotein, alpha-fetoprotein variants, abnormal prothrombin once a month. Imaging examination includes liver ultrasonography once a month, liver MR or CT scanning every 3 months, lung CT every 3 months.
- Multidisciplinary teams determine whether tumors recur based on imaging and serological examinations.
- The follow up duration time is 5 years.
- The primary endpoint is tumor recurrence which refers to the time from treatment to tumor recurrence. Overall survival refers to the time from treatment to death for any reason. The 1, 3, 5-year recurrence-free survival rate and the 1, 3, 5-year overall survival rate will be analyzed.
- The side effects during treatment were recorded. At the same time, patients' status will be scored according to ECOG PS score. Acute or subacute toxicity is classified as level of 0-4, 0 as non-response, 1 as mild, 2 as moderate, 3 as

severe and 4 as life-threatening. The severity of adverse events was judged, reported and handled according to GCP requirements of clinical trials.

5. Safety

Lenvatinib is a clinically approved drug. This study will be conducted in strict accordance with drug specifications and doses.

6. Data analysis and statistical methods

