6.2 Statistical Methods

The researcher is responsible for checking and preserving all the data, and handing over the data results to professional statisticians for analysis. Survival curves are estimated using the Kaplan – Meier method. For identification of independent prognostic factors, the Cox proportional hazard model was used in the univariate and multivariate analyses. All statistical analyses were performed using the SPSS (version 22.0). Statistical significance was defined as $p < 0.05$.

7. Emergency Event Management

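### Section 8 gives the monitoring plan as None, and the available text assigns no one to compare accumulating harm between arms before the trial ends

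*Combined protocol and SAP*

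**What the plan says.** Section 1 states the aim as to "observe the efficacy and safety of lenvatinib in preventing high-risk recurrence of hepatocellular carcinoma patients after liver transplantation". Safety is therefore a stated purpose of the trial.

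The safety provisions in the available text are:

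- **Section 2:** monthly serum and imaging checks, partly to monitor lenvatinib side effects. On toxicity it says: "When side effects of lenvatinib occur, the dosage can be reduced", down to discontinuation. Section 4.3 also allows delay or reduction.
- **Section 3.4:** conditions under which an individual stops the drug and leaves the study.
- **Section 4.4:** "The side effects during treatment were recorded", toxicity is classified from level 0 to 4, and "The severity of adverse events was judged, reported and handled according to GCP requirements of clinical trials".
- **Section 6.2:** "The researcher is responsible for checking and preserving all the data", after which results go to statisticians. The methods listed are Kaplan-Meier curves, Cox models and a significance level of 0.05. No safety summary is listed.
- **Section 7.2:** a designated person "is responsible for medical emergencies and related treatment", and large-scale or critical events are to be reported to the department head and the hospital.
- **Section 8:** headed "8. Data security and monitoring plan". The whole entry is the word None.

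**The concern.** Nearly all of these provisions act on one patient at a time. The exception is the escalation route in section 7.2. It reaches above the individual, but it is unscheduled and does not compare arms.

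That matters in this population. Lenvatinib starts 1 to 2 months after transplantation in patients on multi-drug immunosuppression, so serious events can be expected in both groups. A clinician handling single cases, however carefully, cannot easily tell an excess from background. The trial has a concurrent randomised control group that could supply the comparison, but the plan schedules no use of it for safety.

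With recruitment planned over 12 months, an excess that only a comparison would reveal could go unrecognised until all 54 lenvatinib patients have been exposed. Section 4.4 gives a follow-up of 5 years, so treated patients could also go a long time without such a review.

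**Working it through.** The plan gives no monitoring figure to reproduce. The check asks when a look would fall, what could prompt review, and how much a by-arm table could show.

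**Inputs from the documents.** 54 patients per group (section 2; section 6.1 says 53), 1:1 allocation and 12 months of recruitment (section 6.1).

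**Assumptions.** Uniform accrual, 3 months of follow-up before a patient counts, and illustrative event rates. The documents give no event rates.

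**1. Timing.** The lenvatinib accrual rate is 54/12 = 4.5 per month. A look after *k* lenvatinib patients have 3 months of follow-up falls at month *k*/4.5 + 3, with *k* + 3 × 4.5 = *k* + 13.5 enrolled.

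| *k* | Month of look | Lenvatinib patients enrolled | Not yet enrolled |
|---|---|---|---|
| 18 | 4 + 3 = 7 | 31.5 | 22.5 |
| 27 | 6 + 3 = 9 | 40.5 | 13.5 |
| 36 | 8 + 3 = 11 | 49.5 | 4.5 |

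Using 53 per group (53/12 = 4.42 per month) gives 31.25 and 49.25 enrolled at *k* = 18 and 36, which is no material change. A look at 18 can still spare patients a first exposure. A look at 36 mainly serves those already on treatment.

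**2. Would harm have appeared by mid-accrual?** About 27 lenvatinib patients are enrolled by month 6. The chance of at least one case is 1 − (1 − *p*)^27, which is 75% at *p* = 5% and 94% at *p* = 10%. Cases would probably exist by then. What is missing is a scheduled comparison.

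**3. Is a count in the lenvatinib arm alone a usable trigger?** Binomial probabilities of reaching the count:

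| True rate | 3 or more of 18 | 5 or more of 36 |
|---|---|---|
| 3% | 1.6% | 0.4% |
| 5% | 5.8% | 3.2% |
| 10% | 26.6% | 28.9% |
| 15% | 52.0% | 64.5% |
| 20% | 72.9% | 87.3% |

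If the background rate is 10%, these counts occur 27% and 29% of the time with no drug harm. They discriminate well only if background is near 3%, which nothing in the documents supports. The trigger should therefore be a difference between arms.

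**4. What can a by-arm comparison detect?** Power of a two-sided Fisher test at 5%:

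| Lenvatinib vs control | 18 per arm | 36 per arm |
|---|---|---|
| 20% vs 10% | 6% | 14% |
| 20% vs 3% | 18% | 48% |

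A formal test at these sizes would miss most modest excesses. The tables are for judgement against a difference agreed in advance, not for significance testing.

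**The case against.** The strongest case against is that safety is not neglected here. The trial is open and single-centre. Patients are checked monthly, dosing can be reduced to discontinuation, and section 7.2 escalates large-scale or critical events. Investigators who know the allocation may notice a problem informally, and early by-arm tables have little power. All of this stands, and it limits the point to a missing scheduled comparison.

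A reader might infer more, and the documents do not support it:

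- **That no one reviews harm at all.** Patient-level review is described. In addition, text between sections 6.2 and 7.2, probably section 7.1, was not available and may deal with event reporting. Nothing can be said about what it contains.
- **That section 8 contradicts the GCP sentence in section 4.4.** That sentence concerns handling of individual adverse events, which can coexist with having no separate monitoring plan. This is a gap, not a contradiction.
- **That section 7.2 covers single emergencies only.** Its wording extends to large-scale events.
- **That an independent monitoring committee is required.** The text gives no basis for that in a single-centre trial of 108 patients. A named recipient and a schedule would close the gap.
- **That the researcher alone controls recurrence dates.** Section 4.4 assigns the determination of recurrence to multidisciplinary teams.

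**Conclusion.** The point holds as a gap in planned oversight that should be closed. Section 8 explicitly declines a monitoring plan, safety is part of the aim, and no by-arm review of accumulating harm is scheduled in the available text. The heading of section 8 also covers data security, but it names monitoring too, and no monitoring plan appears elsewhere in that text.

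The practical size is the number of patients an early look could still protect: about 22 to 23 of 54 lenvatinib patients not yet enrolled at month 7, but only 4 to 5 at month 11. These figures rest on uniform 12-month accrual and a 3-month follow-up requirement. The event-rate figures are illustrations only. The benefit is better-organised judgement about harm, not a high probability of statistical detection.

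**What to change.** Replace None in section 8 with the following.

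1. **Content and route.** Scheduled tables of deaths and level 3-4 toxicity by arm, graded the same way in both arms. The statisticians of section 6.2 prepare them and send them to the department head and hospital of section 7.2 and to the ethics committee.
2. **Timing.** The first table when 18 lenvatinib patients have 3 months of follow-up (near month 7). The second should come earlier than 36 such patients; 27, near month 9, is one example. If it is kept at 36, it should be described as protecting patients already on treatment.
3. **Trigger.** The sponsor fixes in advance the between-arm difference that prompts formal review, not a count in one arm.
4. **Limits.** No recurrence comparison and no efficacy test is made at these looks, so the final 5% test needs no adjustment.

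As a separate minor point, recurrence and death dates should be locked before the final comparison is run.

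**Cost.** New wording for section 8 and two short tables by existing staff. Reviewers will see interim deaths by arm, and overall survival is an endpoint in section 4.4, so circulation should be kept to the named recipients. A review may cause a short wait. Adding graft loss would need new data collection, because the available text does not list it as a recorded item.
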